5.2 Selection of subjects

5.2.1 Inclusion criteria

- 1) Age >or equal to 18, no limitation on gender;
- 2) Hospitalized patients;
- 3) Patients who are anticipated to need or have vascular access catheter devices [This may include: Peripheral Intravenous Catheter (PIVC), Central Venous Catheter (CVC) and Peripherally Inserted Central Catheter (PICC)];
- 4) Patients who are expected to require flushing the vascular access catheter with saline at the beginning, during, or end of infusion therapy, or who require flush and/or lock vascular access catheters at the beginning, during, the end of drug therapy;
- 5) Patients who can understand the purpose of the trial, agree to participate in this clinical trial and voluntarily sign the informed consent form.

5.2.2 Exclusion criteria

- 1) Patient reports pregnancy or lactation (self-report);
- 2) Subjects who are known to have blockage or recanalization of vascular access prior to this trial;
- 3) Subjects who are known to have uncomfortable symptoms such as redness and pain, or common complication associated with indwelling catheter such as phlebitis and infection at the localized insertion site prior to this trial;
- 4) Patient who has participated in a drug or medical device clinical trial within three months before enrollment;
- 5) Any other situation that, in the opinion of the Investigator would make the patient considered unfit for this study.

5.2.3 Criteria and procedures of subject withdrawal

5.2.3.1 Investigator-decided withdrawal

If subjects enrolled have conditions during the study that the investigator considers inappropriate for continuation of the study, the subject needs to withdraw from the study.

5.2.3.2 Subjects voluntarily withdraw from the study

According to the provisions of the informed consent form, subjects have the right to withdraw from the study at any phase of the study, or the subjects do not explicitly propose to withdraw from the study, but they no longer receive flush syringe treatments or examinations and are lost to follow-up, which is also a category of "withdrawal" or "drop-out".

For subjects withdrawing from the trial for any reason, it is required to record reasons for their withdrawal as far as possible, complete and report all observations in detail.

5.2.3.3 Withdrawal (drop-out) handling

Drop-out refers to any subject who has signed the informed consent form (ICF), has passed the screening, and is enrolled in the clinical trial randomly but withdraws from the clinical trial at any time for any reason is considered a drop-out case.

For subjects who drop out of this trial, the reasons for withdrawal from the trial and the completed operations before drop-out shall be documented.

If the subject withdraws from this trial due to adverse events, timely and appropriate flush syringe treatments and follow-up examinations shall be performed until the adverse events are recovered (return to normal state or to baseline state), or until the condition is stable, or until a reasonable explanation is available.

5.2.4 Suspension / Termination criteria of study

The major purpose of suspending/terminating the study is to protect the rights and interests of the

subjects, ensure the quality of the trial and avoid unnecessary economic losses. Reasons for suspension/early termination of the study are as follows:

- 1. The sponsor may suspend/terminate the study for any scientific, medical or ethical reasons, but must fully consider the rights, safety and health of the subjects in the group;
- 2. The sponsor voluntarily requests suspension/termination for other reasons;
- 3. Drug authority, ethics committee, sponsor or investigator consider that there are significant safety risks;
- 4. Other reasons judged by the sponsor or investigator that are considered inappropriate to proceed with the trial.

The suspension arising therefrom can be a permanent "termination" or a temporary "suspension". The study can be restarted after the problem that caused the suspension of the study is resolved. Suspension/termination of the study or restarting the study after suspension must be reported to the Ethics Committee.

5.3 Evaluation method

5.3.1 Evaluation of effectiveness

5.3.1.1 Primary efficacy indicators and evaluation time

> Overall performance of flushing and/or locking catheters

Definition: The success rate of the prefilled flush syringes for flushing and/or locking the catheter.

Observation time: Flushing and/or locking the catheter during preparation, initiation, implementation, termination.

Evaluation criteria: The success rate of flushing and/or locking the catheter = (number of cases evaluated as "successful"/total number of cases evaluated) $\times 100\%$.

Evaluation method:

Overall performance is assessed by a Nurse, who need to answer the following questions:

- 1) Can air in the BD Pre-filled Flush Syringes be expelled successfully?
- 2) Can BD Pre-filled Flush Syringes be connected to the catheter smoothly?
- 3) Can BD Pre-filled Flush Syringes flush and /or lock the catheter successfully?
- 4) Can BD Pre-filled Flush Syringes disconnect from the catheters smoothly?
- 5) Any leakage observed at any part of the Flush syringe at any time during the usage?

Overall performance for flushing and/or locking the catheter is only considered as "**success**" if: Question 1 to 4 answered with "YES", and question 5 answered with "NO".

Justifications of indicators selected: The effectiveness of this product is mainly reflected in five aspects: priming, connection, flushing and/or locking catheters, disconnection from catheters and leakage.

Cautions: None.

5.3.1.2 Secondary efficacy indicators and evaluation time

> Easy pushability of the plunger when flushing and/or locking.

Definition: Whether the plunger can be easily pushed forward when the pre-filled flush syringe is flushing and/or locking?

Observation time: Flushing and/or locking the catheter during implementation,

termination.

Evaluation criteria: The pushability of the plunger when flushing and/or locking = (number of cases evaluated with score \geq 3 points/total number of cases evaluated) × 100%.

Evaluation method:

Pushability will be assessed by a Nurse, who needs to score the following question:

1) Is the plunger easy to push forward when flushing and/or locking (pushability)?

5-point scale will be used:

- 5 points: Very easy;
- 3 points: Easy;
- 1 point: Difficult.

5.3.2 Safety evaluation

Observation purpose: To evaluate the safety of the pre-filled flush syringe for flushing and/or locking the end of catheter line.

(1) Safety

> Adverse events and serious adverse events

(2) Method and time selection for evaluating, recording and analyzing safety indicators

1) Evaluation method (calculation formula)

• Calculate the incidence of adverse events, serious adverse events: number of subjects experiencing the above events/total number of subjects \times 100%.

2) Time selection

Adverse events/serious adverse events are recorded at all times.

3) Analytical method

See section 6.4 for statistical analysis method.

5.3.3 Other evaluations

(1) Device defects

Device defects that occur during the trial.

(2) Method and time selection for evaluating, recording and analyzing safety indicators

1) Evaluation method (calculation formula)

• Calculate the incidence of device defects: subjects experiencing the above events/total number of subjects × 100%.

2) Time selection

Device defects are recorded at all times.

3) Analytical method

See section 6.4 for statistical analysis method.

5.4 Investigational medical device and control medical device

Investigational group device

Product name:	Pre-filled flush syringes
Specification/Model:	BD 10mL PosiFlush Pre-filled Flush Syringes

Registrant:	BD Medical Technology (Jiangsu) Co., Ltd.	
Shelf life:	3 years	
Storage conditions:	15°C-25°C. It can be extended to 15°C-30°C; do not freeze.	
Intended use:	Used to lock and flush the end of a catheter. It is not suitable for subcutaneous injection and intramuscular injection.	
Product composition:	The product consists of barrel, plunger, plunger stopper, nozzle cap and 0.9% sodium chloride injection (conforming to ChP and USP).	

Control group device

Product name:	BD Pre-filled Flush Syringes		
Specification/Model:	BD 10mL PosiFlush Pre-filled Flush Syringes		
Registrant:	Becton, Dickinson and Company		
Agent:	Becton Dickinson Medical Devices (Shanghai) Co., Ltd.		
Registration Certificate No.:	GXZJ20163142809		
Shelf life:	3 years		
Storage conditions:	20°C-25°C. It can be extended to 15°C-30°C; do not freeze.		
Intended use:	Intended to lock and flush the end of the catheter line at the intervals of different drug treatment. It is not suitable for subcutaneous injection and intramuscular injection.		
Product composition:	The product consists of barrel, plunger, plunger stopper, nozzle cap and 0.9% sodium chloride injection (conforming to USP).		

5.5 Trail procedures

5.51 Trial flow chart

Item Time	Screening period (D-2,-1,0)	Flush syringe treatment period (D1)	Follow-up period (1h after the flush syringe treatment)
Sign the informed consent form	A		
Hospital admission diagnosis/demographic data	A		
Review inclusion/exclusion criteria			
Randomization			
Vital signs ¹			
Evaluation of effectiveness			
Record adverse events/serious adverse events ²	A		
Record combined medications/treatments ³	A		
Device defects			

Note: The screening period and the treatment period can be the same day.

- 1. Vital signs: Record the recent last examination result prior to the flush syringe treatment.
- 2. Record adverse events: Collect and record the adverse events in each subject during the period from the signing the informed consent form to the termination of follow-up. Investigator should follow up the adverse events, follow up the subject undergoing such adverse events until the adverse events are recovered (return to normal state or to baseline state), or until the condition is stable, or until a reasonable explanation is available.
- 3. Combined medication/treatment: Collect and record the combined medication before and after the use of the study device during the trial (the closest one to such use, twice in total), and the medication and the study device shall pass through the same vascular access (excluding oral medication); medication/treatment for adverse events.

5.5.2 Implementation of the trial

Subjects will be trained for the use of Pre-filled flush syringes prior to enrollment. Investigators using the device (Investigational group device and/or Control group device) shall be specialized in intravenous infusion therapy for at least 2 years; maintain peripheral or central vascular access more than 10 times per month for the last 6 months; complete the product use of pre-filled flush syringes as required and complete assessment after training.

The informed consent form shall be signed by each subject before screening. Refer to the "trial flow chart" for the specific trial process.

This clinical trial is divided into three phases: screening period, flush syringe treatment period and follow-up period:

The first phase is the screening period with a maximum of 3 days. The screening period and the flush syringe treatment period can be the same day. During the screening period, a visit will be set up to review the inclusion/exclusion criteria of the subjects to ensure that the subjects meet the enrollment conditions. All selected subjects shall be randomly assigned to the investigational group or the control group in a ratio of 1:1.

The second phase is the flush syringe treatment period. During this period, a fixed visit is set up on the day of the flush syringe treatment to complete the operation of the treatment and record the effectiveness and safety as per the protocol.

The third phase is the follow-up period. A follow-up shall be performed at 1 hour after the flush syringe treatment.

The visiting investigators shall be required to observe, treat and record the subjects in each phase according to the flow chart.

Screening period (D-2,-1,0)

- 1) Sign the informed consent form (Note: Relevant screening examinations shall not be performed before the written informed consent form is obtained);
- 2) Demographic data collection: date of birth, gender, ethnicity, etc.;
- 3) Hospital admission diagnosis;
- 4) Register the subject screening number of the selected patients, and review the subject inclusion and exclusion criteria;
- 5) Randomization;
- 6) Vital signs: Respiration, blood pressure (systolic pressure, diastolic pressure), pulse, body temperature;
- 7) Record adverse events and serious adverse events;
- 8) Record combined medications/treatments.

Flush syringe treatment period (D1)

Flush syringe treatment period indicates the use and operation of pre-filled catheter flush syringes.

1) The operation shall be performed to flush and/or lock the end of the catheter line:

The procedure shall be performed to flush and/or lock the end of the catheter line by the study nurse. Refer to section 3.3.8 Usage for the specific operation method.

Record the time to start and end the flush syringe treatment.

Before the priming preparation, if device defects and other problems are found, each subject can change a new study device; if such problems are found after the priming preparation, each subject can only use the current one without changing the device.

2) Evaluation of effectiveness:

The use of the pre-filled flushing syringe shall be evaluated by the study nurse after flushing and/or locking the end of the catheter line. Refer to section 5.3.1 Evaluation of effectiveness for the specific evaluation method.

- 3) Record adverse events (AE/SAE);
- 4) Record combined medications/treatments;
- 5) Record device defects.

Follow-up

Follow-up is performed at 1 hour after the flush syringe treatment.

- 1) Record adverse events (AE/SAE);
- 2) Record combined medications/treatments.

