5.1 Overall design and determination basis

Overall design

Selection of trial method: this trial is a prospective, multi-center, randomized, open, parallel-controlled clinical trial. The investigational product is the Pre-filled Flush Syringes (specification and model: BD 10 mL PosiFlush pre-filled flush syringes), and the control product is the BD Pre-filled Flush Syringes (specification and model: BD 10 mL PosiFlush pre-filled flush syringes), a statistical design will be performed using non-inferiority statistical comparisons.

Prospective: The study method with signed informed consent form as the starting point and follow-up to 1 hour after the end of the catheter locking and flushing treatment.

Randomization: A block randomization method is used and SAS9.4 or above software is adopted to generate the random assignment list for subjects. After confirming that the subjects meet the eligibility evaluation of the inclusion and exclusion criteria, the investigator or authorized personnel logs in to the randomization system to obtain the random number and corresponding group information, then the study nurses perform the trial intervention according to the random assignment results.

Open: Due to the difference in the appearance between the investigational product and the control product (the printing on the smallest package is inconsistent), and the use of incomplete packaging is prohibited, the investigators and subjects cannot be blinded in the trial, so an open design is used for this trial.

Parallel control: Because there are already equivalent products on the market, the design of parallel control is selected. The equivalent products are the BD Pre-filled Flush Syringes with proven efficacy and safety.

Multi-center: Three institutions with clinical trial qualifications are selected to carry out this clinical trial. The subjects are enrolled in multiple sites and come from a wide range of subjects to avoid the bias of trial results caused by systematic errors at a single site.

Non-inferiority test: To evaluate that the overall performance of the pre-filled flush syringes for flushing and/or locking the catheter is non-inferior to that of the BD Pre-filled Flush Syringes.

After signing of informed consent form, all subjects who meet the inclusion criteria and do not meet the exclusion criteria are randomized into the investigational group or control group in a 1:1 ratio.

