6.1 Estimation of sample size

A total of 378 subjects are proposed to be enrolled in this clinical trial. This study is a non-inferiority design with parallel control. The equivalent products already available on the market (BD Pre-filled Flush Syringes) are selected as the control group device. The study intends to investigate that the overall performance of the investigational device group device for flushing and/or locking the catheter is non-inferior to that of the control group device. According to previous clinical experience, the overall performance success rate of equivalent devices for flushing and/or locking catheters is about 98%. Hence, it is assumed that the treatment completion rate of the investigational device group is consistent with that of the equivalent device. This study adopts a non-inferiority design, with α =0.025 (one-sided), β =0.1 (power of test of 90%), and the non-inferiority margin of 5%. The subjects in the investigational device group and the control group are allocated in an equal ratio of 1:1. The sample size shall be calculated to each enroll 165 subjects into the investigational device group and the control group by using the PASS software. However, 368 subjects shall be included to participate in this clinical study considering factors such as drop-out of subjects (drop-out rate of 10%) during the trial and other factors.

This study will be performed by 63 authorized nurses who participate in using the study device, each nurse will randomly use 3 investigational devices and 3 control devices, so a total of 378 subjects will be proposed to be enrolled in this clinical trial.

Minimum and maximum number of subjects and reasons for each clinical trial institution

This trial will be conducted simultaneously in multiple clinical trial institutions to enroll subjects. In principle, the subjects enrolled at each site will be distributed as evenly as possible to ensure adequate site representation. However, given the feasibility and enrollment progress, the number of subjects enrolled at each site will be properly adjusted according to the actual situation, so as to ensure the relative balance of the enrollment size of each site, and the final enrollment size of a particular site shall not exceed 50% of the total number of cases, and at least not less than half of the number of cases borne by the average distribution.

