6.5.2 Flush syringe treatment assignment or randomization

The random number of the subject will be provided by the statistical analysis unit commissioned by the sponsor, and the random assignment table of the subject will be generated using SAS9.4 or above. Given the number of seeds and block length, subjects are randomly assigned to the trial and control groups in a 1:1 ratio through a block randomization method.

The random number of the subjects is a 3-digit "site number". If the serial number is less than 3 digits, "0" is added to the front so as to make up 3 digits.

Subject randomization is completed by an Interactive Web Response System (IWRS). Systematic randomization work will be carried out by the investigator or relevant personnel authorized by the investigator. After the successful screening of subjects in each center, the investigators or other authorized personnel log in to the randomization system to obtain the random number and corresponding group information, then study nurses perform the trial intervention according to the random assignment results.

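### Randomisation is listed in a screening period of up to 3 days, ahead of syringe use, so subjects lost after an open allocation leave the primary analysis

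*Protocol*

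**What the plan says.** **Timing.** Protocol 5.5.2 states: "The first phase is the screening period with a maximum of 3 days". Its task list for days D-2, -1 and 0 contains "5) Randomization", and the D1 list has no such step. The same section adds: "The screening period and the flush syringe treatment period can be the same day". It does not require this. SAP 3.4 repeats the arrangement.

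**Open allocation.** Protocol 5.1 says "the investigators and subjects cannot be blinded in the trial, so an open design is used for this trial". Under protocol 6.5.2, site staff "log in to the randomization system to obtain the random number and corresponding group information", so the arm is known to them from that moment.

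**Eligibility.** Protocol 5.2.1 admits "Patients who are anticipated to need or have vascular access catheter devices". The next criterion asks for an expected need to flush or lock, not one already due.

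**Handling of a subject never flushed.** In SAP Table 6.1 (Scenario 1), a subject with no effectiveness evaluation has a missing primary outcome and is in the FAS but not the PPS. The PPS is the primary population (protocol 6.2, SAP 5.2). The primary outcome is not imputed (SAP 7.1), and percentages use non-missing data only (SAP 6.1). SAP 6.2.1 tabulates by group the randomised subjects who did not use the device.

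**The concern.** Each syringe is used once, the nurse scores it directly afterwards, and follow-up lasts 1 hour. A trial of this kind can run with almost no interval between allocation and outcome. Here an interval is permitted, the arm is known throughout it, and some entrants may turn out not to need a flush. A subject lost in that interval has been allocated but contributes nothing to the primary success rate.

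Two things are at stake. The first is precision, because an allocation is spent without an observation. The second is comparability. If staff who know the arm could influence which subjects go on to the study flush, the evaluated groups would no longer be those that randomisation formed. Later randomisation removes both problems at little cost.

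**Working it through.** **1. The plan's own sample size.** Inputs from the protocol synopsis and 6.1: success 98% in both arms, margin 5 points, one-sided alpha 0.025, power 90%, 1:1 allocation, attrition 10%.

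- n per arm = (z₀.₉₇₅ + z₀.₉₀)² × 2 × 0.98 × 0.02 / 0.05² = 164.76, rounded up to 165.
- With attrition: 165 / 0.90 = 183.3, rounded up to 184 per arm, or 368 in total.
- Nurse scheme: 63 × 6 = 378, or 189 per arm.

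All three totals match the plan.

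**2. The permitted gap.** By the day labels, randomisation on D-2 and use on D1 are 1 − (−2) = 3 days apart. With same-day use the gap can shrink to almost nothing. No other limit on the time from randomisation to use is stated.

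**3. The path of a subject randomised but never flushed.**

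| Step | Result | Source |
|---|---|---|
| Effectiveness evaluation | Not performed | SAP Table 6.1, Scenario 1 |
| Primary outcome | Missing, not imputed | SAP Table 6.1, SAP 7.1 |
| PPS (primary) | Excluded | Protocol 6.3, SAP 5.2 |
| FAS | Included by name, outside the denominator | SAP 6.1, Table 6.1 |

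The FAS row has a qualification. The code printed in SAP 6.3.1 for the site-adjusted difference sets every record that is not a pass to the non-pass value, which would include a missing one. Text and code disagree for the FAS and need reconciling. The PPS is unaffected.

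**4. Effect on power.** A loss of 10% is 0.10 × 378 = 37.8, about 38 subjects, which leaves 189 × 0.90 = 170.1, or 170 per arm. Exact power sums the binomial probabilities, at 98% in both arms, of all outcomes with Wald lower limit above −5%:

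p̂₁ − p̂₂ − 1.96 × √[p̂₁(1 − p̂₁)/n + p̂₂(1 − p̂₂)/n] > −0.05

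| Evaluated per arm | Exact power, Wald | Normal approximation |
|---|---|---|
| 165 | 89.8% | 90.0% |
| 170 | 89.1% | 90.9% |
| 189 | 91.9% | 93.5% |

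The difference between 170 and 189 is 91.9 − 89.1 = 2.8 points exact, and 93.5 − 90.9 = 2.6 by the approximation. Exact power does not rise smoothly with n, which is why 165 sits slightly above 170. The difference is therefore an order of size. It is also a ceiling, because it assumes that all attrition disappears.

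**The case against.** **The power is already budgeted.** This stands. The requirement is 165 per arm, and 170 remain after the planned 10% loss. The precision argument alone would not justify a change.

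**The 10% is not shown to come from this gap.** This also stands. A reader might infer that the gap is the main source of attrition, since little else can go wrong in a single use with 1-hour follow-up. But protocol 6.1 attributes the allowance to drop-out and other factors without a breakdown, and protocol 5.2.3 counts withdrawal at any time and for any reason. Unanswered or not-applicable items also remove subjects from the PPS. Later randomisation would not prevent all of these.

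**Differential loss is not shown.** Both products are 10 mL pre-filled saline syringes, and the stated obstacle to blinding is the printing on the smallest package. Whether a patient comes to need a flush should hardly depend on the syringe allocated. Loss unrelated to arm and to likely outcome costs precision only. What remains is that the open interval permits arm-related loss.

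**A worst-case imputation looks alarming but proves little.** Suppose that 4 test-arm subjects are lost from 189 per arm. Left out (181/185 vs 185/189), the Wald lower limit is −2.98%. Counted as failures (181/189 vs 185/189), it is −5.64%, beyond the margin. A reader might infer that a few losses would overturn the conclusion. The loss count is an assumption, and a syringe never opened is not a device failure.

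**Other intervals would show lower power.** The SAP plans Wald and uses Newcombe-Wilson only when both arms are at 100%, so power under other intervals is not a measure of this point.

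**Safeguards exist.** Same-day use is allowed, an expected need to flush is required, and non-use is tabulated by group. The tabulation would reveal an imbalance, but only afterwards.

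**Conclusion.** The point holds as a cheap improvement to the design, not as a defect that threatens the conclusion. The documents place randomisation in the screening period, allow but do not require same-day use, disclose the arm at allocation, and drop subjects never flushed from the primary analysis.

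The measurable gain is at most about 3 points of exact power with the planned Wald interval, given 98% success in both arms and the avoidance of all attrition. The true gain depends on the rate of loss between randomisation and use, which the documents do not give. Protection against arm-related loss is the better reason for the change, but such bias is a possibility that the documents neither establish nor allow to be quantified.

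**What to change.** Keep consent and eligibility review in the screening period. Move randomisation to D1, immediately before the syringe is opened, once the catheter is in place and a flush is due. Align the flow chart and the text of protocol 5.5 (the first-phase paragraph and both task lists) with SAP 3.4 and its Table 3.1. The statements in protocol 5.1 and 6.5.2 and SAP 3.1 that randomisation follows confirmed eligibility can stand, but should be checked against the new timing. So should the scheme of 3 + 3 devices for each of 63 nurses.

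The cost is a small edit to both documents and IWRS access at the point of use. The system is already web-based. While the SAP is open, its rule for missing outcomes in the FAS should be reconciled with the printed code.
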